# 10 Reporting

# 10.1 Final Study Report

All information regarding this clinical study must be kept in confidence. The statistical analysis and the integrated final study report will be prepared according to ICH E6 and finalized within 12 months after the Last Patient Last Visit (LPLV) took place. The final study report will be reviewed and signed by the Sponsor, the Coordinating Investigator and all further responsible persons. All information in that report is strictly confidential.

# 10.2 Publication/Data sharing Policy

The Investigator/Institution will not publish the results of the trial without the prior written consent of the Sponsor, which permission shall not be unreasonably withheld. If the Sponsor grants such permission, the Investigator/Institution agrees to submit a copy of any manuscript and/or abstract to the Sponsor for review and comment at least 90 days prior to its submission for publication. The Sponsor shall have the applicable 90-day period to respond to the Investigator/Institution with any revisions. Investigator/Institution agrees to delete any confidential information identified by the Sponsor at the Sponsor's sole discretion, prior to submitting such manuscript and/or abstract for publication. If reasonably requested by the Investigator/Institution, the Sponsor will take reasonable steps to expedite the review process to less than the 90-day period to meet Investigator's/Institution's publication deadlines, but the Sponsor is under no obligation to expedite the review process. Upon notification by the Sponsor that such review has been completed, Investigator/Institution may submit the manuscript and/or abstract for publication agrees. Upon notification by the Sponsor that such review has been completed, Investigator/Institution may submit the manuscript and/or abstract for publication after deleting any confidential information identified by the Sponsor.

# 11 Ethical and Regulatory Aspects

# 11.1 Good Clinical Practice and Declaration of Helsinki

The procedures set out in this study protocol are designed to ensure that the Sponsor and the Investigator abide the principles of ICH E6 recommended for adaptation in June 2015 by the ICH Steering Committee and according to the Declaration of Helsinki of 2013 concerning the conduct, evaluation and documentation of the study. The study will also be performed adhering the local legal conditions and requirements. Each Investigator must confirm this by signing the study protocol.

# 11.2 Approval of the Study

Prior to study start, the study protocol and/or other appropriate documents will be submitted to the relevant ECs and CAs for approval. Approval from all concerned ECs and CAs must be obtained before starting the study.

### 11.3 Insurance

During their participation in the clinical trial the patients will be insured as defined by legal requirements. The sponsor is providing insurance to indemnify (legal and financial coverage) the investigator/trial centre against claims arising from the study, except for claims that arise from malpractice and/or negligence. The compensation of the subject in the event of study-related injuries will comply with the applicable regulations.

# 11.4 Confidentiality

All local legal requirements regarding data protection will be adhered to. All study findings and documents will be regarded as confidential. The Investigator and members of the research team must not disclose any information without prior written approval from the Sponsor. The pseudonymity of patients participating must be maintained. Throughout documentation and evaluation, the patients will be identified on CRFs and other documents by a patient IDs. Documents that identify the patient personally (e.g., the signed informed consent, patient identification list) must be maintained in confidence by the Investigator. *The patients will be informed in the ICF that all study findings will be stored on paper and handled in strictest confidence*.

# 12Amendments

Amendments must be submitted to the appropriate CAs and ECs. Substantial amendments may be implemented only after CA/EC approval has been obtained. Urgent amendments that are intended to eliminate an apparent immediate hazard to subjects may be implemented prior to receiving CA/EC approval. However, approval must be obtained as soon as possible after implementation. Therefore, the sponsor must inform the CA and the EC concerned of the new events, the measures taken and their plan for further action as soon as possible.

# 14 Supplements/Appendices

14.1 Appendix 1: Toxicity Grading Scale vaccine in clinical trials

Local Reaction to Injectable Product	-	Moderate (Grade 2)	Severe (Grade 3)	Potentially Life Threatening (Grade 4)
Pain		Repeated use of non-narcotic pain reliever > 24 hours or interferes with activity	Any use of narcotic pain reliever or prevents daily activity	Emergency room (ER) visit or hospitalization
Tenderness	Mild discomfort to touch	Discomfort with movement	Significant discomfort at rest	ER visit or hospitalization
Erythema/Redness *	2.5 - 5 cm	5.1 - 10 cm	> 10 cm	Necrosis or exfoliative dermatitis
Induration/Swelling **	does not	5.1 - 10 cm or interferes with activity	> 10 cm or prevents daily activity	Necrosis

### A. Tables for Clinical Abnormalities

\* In addition to grading the measured local reaction at the greatest single diameter, the measurement should be recorded as a continuous variable. \*\* Induration/Swelling should be evaluated and graded using the functional scale as well as the actual measurement.

Vital Signs *	Mild (Grade 1)	Moderate (Grade 2)	Severe (Grade 3)	Potentially Life Threatening (Grade 4)
Fever (°C) ** (°F) *	38.0 – 38.4 100.4 – 101.1	38.5 – 38.9 101.2 – 102.0	39.0 – 40 102.1 – 104	> 40 > 104
Tachycardia - beats per minute	101 – 115	116 – 130	> 130	ER visit or hospitalization for arrhythmia
Bradycardia - beats per minute***	50 – 54	45 – 49	< 45	ER visit or hospitalization for arrhythmia
Hypertension (systolic) - mm Hg	141 – 150	151 – 155	> 155	ER visit or hospitalization for malignant hypertension

Hypertension (diastolic) - mm Hg	91 – 95	96 – 100	> 100	ER visit or hospitalization for malignant hypertension
Hypotension (systolic) – mm Hg	85 – 89	80 – 84	< 80	ER visit or hospitalization for hypotensive shock
Respiratory Rate – breaths per minute	17 – 20	21 – 25	> 25	Intubation

\* Subject should be at rest for all vital sign measurements.
 \*\* Oral temperature; no recent hot or cold beverages or smoking.
 \*\*\* When resting heart rate is between 60 - 100 beats per minute. Use clinical judgement when characterizing bradycardia among some healthy subject populations, for example, conditioned athletes.

Systemic (General)	Mild (Grade 1)	Moderate (Grade 2)	Severe (Grade 3)	Potentially Life Threatening (Grade 4)
Nausea/vomiting	No interference with activity or 1 - 2 episodes/24 hours	Some interference with activity or > 2 episodes/24 hours	Prevents daily activity, requires outpatient IV hydration	ER visit or hospitalization for hypotensive shock
Diarrhea	2 - 3 loose stools or < 400 gms/24 hours	4 - 5 stools or 400 - 800 gms/24 hours	6 or more watery stools or > 800gms/24 hours or requires outpatient IV hydration	ER visit or hospitalization
Headache	No interference with activity	Repeated use of non-narcotic pain reliever > 24 hours or some interference with activity	Significant; any use of narcotic pain reliever or prevents daily activity	ER visit or hospitalization
Fatigue	No interference with activity	Some interference with activity	Significant; prevents daily activity	ER visit or hospitalization
Myalgia	No interference with activity	Some interference with activity	Significant; prevents daily activity	ER visit or hospitalization
Systemic Illnes	Mild (Grade 1)	Moderate (Grade 2)	Severe (Grade 3)	Potentially Life Threatening (Grade 4)
Illness or clinical adverse	No interference with activity	Some interference	Prevents daily activity and	ER visit or hospitalization

event (as defined according to applicable	1 0	requires medical intervention	
regulations)			

### **B.Tables for Laboratory Abnormalities**

The laboratory values provided in the tables below serve as guidelines and are dependent upon institutional normal parameters. Institutional normal reference ranges should be provided to demonstrate that they are appropriate.

Serum *	Mild (Grade 1)	Moderate (Grade 2)	Severe (Grade 3)	Potentially Life Threatening (Grade 4)**
Sodium – Hyponatremia mEq/L	132 – 134	130 – 131	125 – 129	< 125
Sodium – Hypernatremia mEq/L	144 – 145	146 – 147	148 – 150	> 150
Potassium – Hyperkalemia mEq/L	5.1 – 5.2	5.3 – 5.4	5.5 – 5.6	> 5.6
Potassium – Hypokalemia mEq/L	3.5 – 3.6	3.3 – 3.4	3.1 – 3.2	< 3.1
Glucose – Hypoglycemia mg/dL	65 – 69	55 – 64	45 – 54	< 45
Glucose – Hyperglycemia Fasting – mg/dL Random – mg/dL	100 – 110 110 – 125	111 – 125 126 – 200	>125 >200	Insulin requirements or hyperosmolar coma
Blood Urea Nitrogen BUN mg/dL	23-26	27 – 31	> 31	Requires dialysis
Creatinine – mg/dL	1.5 – 1.7	1.8 – 2.0	2.1 – 2.5	> 2.5 or requires dialysis
Calcium – hypocalcemia mg/dL	8.0 - 8.4	7.5 – 7.9	7.0 – 7.4	< 7.0
Calcium – hypercalcemia mg/dL	10.5 – 11.0	11.1 – 11.5	11.6 – 12.0	> 12.0
Magnesium – hypomagnesemia mg/dL	1.3 – 1.5	1.1 – 1.2	0.9 – 1.0	< 0.9
Phosphorous – hypophosphatemia mg/dL	2.3 – 2.5	2.0 – 2.2	1.6 – 1.9	< 1.6
CPK – mg/dL	1.25 – 1.5 x ULN***	1.6 – 3.0 x ULN	3.1 –10 x ULN	> 10 x ULN

Albumin – Hypoalbuminemia g/dL	2.8 – 3.1	2.5 – 2.7	< 2.5	
Total Protein – Hypoproteinemia g/dL	5.5 – 6.0	5.0 – 5.4	< 5.0	
Alkaline phosphate – increase by factor	1.1 – 2.0 x ULN	2.1 – 3.0 x ULN	3.1 – 10 x ULN	> 10 x ULN
Liver Function Tests –ALT, AST increase by factor	1.1 – 2.5 x ULN	2.6 – 5.0 x ULN	5.1 – 10 x ULN	> 10 x ULN
Bilirubin – when accompanied by any increase in Liver Function Test increase by factor	1.1 – 1.25 x ULN	1.26 – 1.5 x ULN	1.51 – 1.75 x ULN	> 1.75 x ULN
Bilirubin – when Liver Function Test is normal; increase by factor	1.1 – 1.5 x ULN	1.6 – 2.0 x ULN	2.0 – 3.0 x ULN	> 3.0 x ULN
Cholesterol	201 – 210	211 – 225	> 226	
Pancreatic enzymes – amylase, lipase	1.1 – 1.5 x ULN	1.6 – 2.0 x ULN	2.1 – 5.0 x ULN	> 5.0 x ULN

\* The laboratory values provided in the tables serve as guidelines and are dependent upon institutional normal parameters. Institutional normal reference ranges should be provided to demonstrate that they are appropriate.

\*\* The clinical signs or symptoms associated with laboratory abnormalities might result in characterization of the laboratory abnormalities as Potentially Life Threatening (Grade 4). For example. a low sodium value that falls within a grade 3 parameter (125-129 mE/L) should be recorded as a grade 4 hyponatremia event if the subject had a new seizure associated with the low sodium value. \*\*\*ULN" is the upper limit of the normal range.

Hematology *	Mild (Grade 1)	Moderate (Grade 2)	Severe (Grade 3)	Potentially Life Threatening (Grade 4)
Hemoglobin (Female) - gm/dL	11.0 – 12.0	9.5 – 10.9	8.0 - 9.4	< 8.0
Hemoglobin (Female) change from baseline value - gm/dL	Any decrease – 1.5	1.6 – 2.0	2.1 – 5.0	> 5.0
Hemoglobin (Male) - gm/dL	12.5 – 13.5	10.5 – 12.4	8.5 – 10.4	< 8.5
Hemoglobin (Male) change from baseline value – gm/dL	Any decrease – 1.5	1.6 – 2.0	2.1 – 5.0	> 5.0
WBC Increase - cell/mm 	10,800 – 15,000	15,001 – 20,000	20,001 – 25, 000	> 25,000
WBC Decrease - cell/mm 	2,500 – 3,500	1,500 – 2,499	1,000 – 1,499	< 1,000
Lymphocytes Decrease - cell/mm 	750 – 1,000	500 – 749	250 – 499	< 250
Neutrophils Decrease - cell/mm 	1,500 – 2,000	1,000 - 1,499	500 – 999	< 500
Eosinophils - cell/mm 	650 – 1500	1501 - 5000	> 5000	Hypereosinophilic

Platelets Decreased - cell/mm 	125,000 – 140,000	100,000 – 124,000	25,000 – 99,000	< 25,000
PT – increase by factor (prothrombin time)	1.0 – 1.10 x ULN**	ï€ 1.11 – 1.20 x ULN	1.21 – 1.25 x ULN	> 1.25 ULN
PTT – increase by factor (partial thromboplastin time)	1.0 – 1.2 x ULN	1.21 – 1.4 x ULN	1.41 – 1.5 x ULN	> 1.5 x ULN
Fibrinogen increase - mg/dL	400 – 500	501 - 600	> 600	
Fibrinogen decrease - mg/dL	150 – 200	125 – 149	100 – 124	< 100 or associated with gross bleeding or disseminated intravascular coagulation (DIC)

\* The laboratory values provided in the tables serve as guidelines and are dependent upon institutional normal parameters. Institutional normal reference ranges should be provided to demonstrate that they are appropriate. \*\* "ULN" is the upper limit of the normal range.

Urine *	Mild (Grade 1)	Moderate (Grade 2)	Severe (Grade 3)	Potentially Life Threatening (Grade 4)
Protein	Trace	1+	2+	Hospitalization or dialysis
Glucose	Trace	1+	2+	Hospitalization forhyperglycemia
Blood (microscopic) - red blood cells per high power field (rbc/hpf)	1 - 10	11 - 50	> 50 and/or gross blood	Hospitalization or packed red blood cells (PRBC) transfusion

\* The laboratory values provided in the tables serve as guidelines and are dependent upon institutional normal parameters. Institutional normal reference ranges should be provided to demonstrate that they are appropriate

#### **VERSION HISTORY**

Version	Date	Description
1.0	11JUN2019	Initial version

#### LIST OF ABBREVIATIONS

[  Ga]	Gallium-68
AE	Adverse Event
AUC(0-inf)	Area under the concentration-time curve from time zero (pre-dose) extrapolated to infinite time
AUC(0-t)	Area under the concentration-time curve from time zero (pre-dose) to some fixed time t
AUC(0-t)/D	AUC(0-t) divided by the dose administered
BC	Breast Cancer
BMI	Body Mass Index
CL	Total systemic clearance for intravenous administration
Cmax	Maximum concentration observed
CR	Complete Response
CRF	Case Report Form
CSR	Clinical Study Report
СТ	Computed Tomography
ECG	Electrocardiography
ECOG	Eastern Cooperative Oncology Group
FAS	Full Analysis Set
FDG	Fluorodeoxyglucose
FU	Follow-up
GRPR	Gastrin-Releasing Peptide Receptor
ICF	Informed Consent Form
IHC	Immunohistochemistry
IMP	Investigational Medicinal Product
MedDRA	Medical Dictionary for Regulatory Activities
NSCLC	Non-Small Cell Lung Cancer
PC	Prostate Cancer
PD	Progressive Disease
PET	Positron Emission Tomography
p.i.	Post injection

РК	Pharmacokinetic
РР	Per Protocol
РТ	Preferred Term
QTcB	QT Corrected by Bazett's Formula
QTcF	QT Corrected by Fridericia's Formula
RR	Respiratory Rate
SAE	Serious Adverse Event
SAP	Statistical Analysis Plan
SAS	Statistical Analysis Software
SCLC	Small-Cell Lung Cancer
SI	Standard International unit
SOC	System Organ Class
SUV	Standard Uptake Value
SUVr	Standard Uptake Value ratio
t 1/2	Half-life
TAC	Time Activity Curve
TEAE	Treatment-emergent Adverse Event
t max	Time of maximum observed drug concentration occurrence
Vd	The apparent volume of distribution of the parent test item in the test system
WHO	World Health Organization

#### **1** INTRODUCTION

The purpose of this document is to provide a description of the statistical methods and procedures to be implemented for the analysis of data from Advanced Accelerator Applications Protocol A005D-E01-201. This document is based on protocol Versions 3.1 dated 06 August 2018 (only applicable for France), 3.0 dated 05 July 2018, and 2.0 dated 14 February 2018. If circumstances arise during the study such that more appropriate analytic procedures become available, the statistical analysis plan (SAP) may be revised. However, any revisions to the SAP (both alternative and additional methods) will be made prior to database lock. Reasons for such revisions will be described in the SAP amendment as well as Clinical Study Report (CSR).

#### 2 OVERVIEW

#### 2.1 Objectives

#### **Primary Objective:**

• To characterize preliminary targeting properties of [Ga]-NeoBOMB1 in patients with malignancies known to overexpress Gastrin-Releasing Peptide Receptor (GRPR).

#### Secondary Objectives:

[figure not shown]
- To assess safety and tolerability of a single diagnostic dose of [Ga]-NeoBOMB1 administered as an intravenous bolus injection.
- To assess the bio-distribution, pharmacokinetics, radiation dosimetry, and absorbed dose critical organs for [Ga]-NeoBOMB1 in a limited number of patients.
- To establish the optimal threshold, expressed as Standardized Uptake Value (SUV), to discriminate Positron Emission Tomography (PET) imaging positive results from negative ones.
- To estimate the [Ga]-NeoBOMB1 PET lesion-based and patient-based imaging performance relative to a comparable standard imaging.
- To estimate [Ga]-NeoBOMB1 PET lesion-based and patient-based diagnostic performance relative to cytology and/or histopathology findings (e.g. IHC).

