dosimetry	acquired static PET images resulting in tissue TACs with quantitative			
	fractions of administered activity. ROIs/VOIs will be drawn over these organs			
	to determine relative radiotracer uptake calculated as a percentage of the			
	injected dose per gram of tissue (%ID/g). Tissue TACs will be generated from			
	the amount of radioactivity in one given tissue considering renal excretion			
	activity.			
	Tissue TACs will be fitted to mono- and bi-exponential curves to yield			
	cumulative activities and residence times will be calculated.			
	Dosimetry calculations will be issued from the analyses of organs receiving			
	the highest dose, identified visually. Urine samples from 0-2h and from 2-4h			
	post-injection will be collected to complete dosimetry and biodistribution			
	assessments.			
	The absorbed dose (µGy/MBq) will be transformed into formal			
	biological equivalent dose for radiation exposure (µSv/MBq) to finally yield			
	an effective radiation dose, a factor between others that could help providing			
	· · · •			
	an estimation of total danger to the whole organism.			
	All patients:			
	Maximum standardized uptake values (SUV max ) will be used to determine the			
	tumour lesions, defined as focal areas of abnormal uptake featuring greater			
$SUV_{max}$ than that of surrounding tissue. The imaging time				
	characterized by the greatest number of lesions will be identified via qualitative visual analysis. Similarly, the greatest SUV values will be determined for each lesion on all scans via semi-quantitative analysis. Malignant-like lesions compatible per tumour type and localisation will be semi-quantified and expressed as SUV mean and SUV max . All lesions will be			
	counted and analyzed by measuring SUV mean and SUV max and relative			
	background.			
	Clinical assessment (surgery, imaging or physical examination) during 3			
	months after IMP injection will be collected if available for patients to			

A005D-E01-201	Page 16 of 73
A005D-E01-201	Page 16 of 73

	correlate the focal uptake of [  Ga]-NeoBOMB1 PET which was not possible be matched to morphological lesions on CT/MRI.			
Safety	Safety assessments including physical examination, vital signs, Electrocardiogram (ECG) with frequency-corrected QT-time (QTc) assessment, routine blood analysis and urinalysis will be performed prior to [  Ga]-NeoBOMB1 administration on all subjects.			

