## Figure 2bis: Overall study flow chart for non-dosimetry group

- 3.2 Study objectives
- 3.2.1 Primary Study Objective
  - To characterize preliminary targeting properties of [Ga]-NeoBOMB1 in patients with malignancies known to overexpress GRPR.
- 3.2.2 Secondary Study Objectives
  - To assess safety and tolerability of a single diagnostic dose of [Ga]-NeoBOMB1 administered as an intravenous bolus injection.
  - To assess the bio-distribution, pharmacokinetics, radiation dosimetry, and absorbed dose critical organs for [Ga]-NeoBOMB1 in a limited number of patients.
  - To establish the optimal threshold, expressed as Standardized Uptake Value (SUV), to discriminate PET imaging positive results from negative ones.
  - To estimate the [Ga]-NeoBOMB1 PET lesion-based and patient-based imaging performance relative to a comparable standard imaging.
  - To estimate [Ga]-NeoBOMB1 PET lesion-based and patient-based diagnostic performance relative to cytology and/or histopathology findings (e.g. IHC).

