### Figure 5: Non-dosimetry group PET imaging flow chart

WB PET/CT: low-dose from the vertex to the upper thighs for attenuation correction followed by a total-body PET examination

Data Reconstruction and Image Analysis

The CT transmission images are used for attenuation correction of the PET emission data. After scatter and attenuation correction, PET emission data must be reconstructed using an attenuation-weighted ordered-subsets maximization expectation approach with 2 iterations and 8 subsets on 128x128 matrices and with a 5-mm Gaussian post-reconstruction filtering.

Semi-quantitative analysis (SUVmax and mean) per tumour type group and time point will be conducted to establish pathological thresholds or pathological/physiological ratio thresholds and determine [Ga]-NeoBOMB1-PET diagnostic performance.

Similarly, organs receiving the highest organ dose (HT) will be identified and radiation doses per organ ( $\mu$ Gy/MBq) as well as effective organ doses ( $\mu$ Sv/MBq) will be computed.

PET data will be transferred to the central imaging center in an anonymized way to protect patient's privacy. A procedure is detailed in a separate central imaging reading center manual provided to each site. Briefly, for data transfer, 4 types of files are generally used: Excel info CONFIDENTIAL v. 3.0 dated 05 July 2018 40/73

file, Excel biokinetic PET/CT data, PET/CT DICOM files and additional files (containing the data of the other tests).

The Excel info file shall include all procedures performed in every patient and relative demographic (age, weight, height, etc.) as well as the Patient's ID.

The Excel biokinetics file shall include all PET/CT non-imaging data (activity data) for the different time points (according to the PET/CT protocol) for every measured organ as well as the measured volumes for each organ in every patient. This information will be transferred as an MS Excel file (for processing) and as printed documents signed by the person in charge (for verification and control).

The DICOM files will contain the anonymized raw PET/CT data (using the internal Patient IDs) plus RT structure DICOM files for the structures drawn for the organs at risk (ROIs).

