#### 7.2 Evaluation of Targeting Properties by Standard Uptake Value (SUV)

Targeting properties of [Ga]-NeoBOMB1 will also be evaluated by PET imaging using tumor uptake. Tumor uptake will be evaluated by the Standard Uptake Value (SUV) at each lesion by PET Imaging. The maximum SUVmean and SUVmax (g/mL) of each lesion will be presented by the lesion location with summary statistics (n, mean  $\pm$  standard deviation, minimum, median, quartiles, and maximum) at scheduled time points overall and split by GRPR positive and negative patients, as well as by tumor type. Dosimetry and non-dosimetry group will be summarized separately due to different scheduled time points.

The 80% and 95% confidence intervals for difference in SUV (SUVmean and SUVmax) between GRPR positive and negative patients will be derived by Student's *t* distribution if normality assumption is adequate, or Wilcoxon Rank Sum method otherwise.

The Standard Uptake Value ratio (SUVr) at each time point will be calculated as the SUVmean of each lesion / the SUVmean of different regions as a reference and presented in a data listing.

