#### 7.4 Diagnostics by [Ga]-NeoBOMB1 Compared with Conventional Imaging

The diagnostic performance of [Ga]-NeoBOMB1 to malignancies (lesions) known to overexpress GRPR will be paralleled with comparable standard imaging modalities such as, but not limited to, FDG-PET. Positive and negative lesions by the two imaging techniques will be cross-tabulated overall and also by localization area on a lesion level and a patient level, where positivity will be assessed visually. Cross-tabulations will also be repeated splitting by GRPR positive and negative patients and also by primary tumor type of patients.

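### The SAP keeps the optimal SUV threshold as a secondary objective but plans no analysis that would produce one, and does not record it as dropped

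*SAP*

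**What the plan says.** **Objective.** SAP section 2.1 and protocol section 3.2.2 both list the threshold; the SAP wording is "To establish the optimal threshold, expressed as Standardized Uptake Value (SUV), to discriminate Positron Emission Tomography (PET) imaging positive results from negative ones". SAP section 2.2 says every objective except biodistribution and dosimetry is assessed in all 50 patients.

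**Intended route.** Protocol section 4.1.6 says semi-quantitative SUV analysis, per tumour type group and time point, "will be conducted to establish pathological thresholds or pathological/physiological ratio thresholds and determine" diagnostic performance. Protocol section 7.2 leaves statistical methods to the SAP.

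**Planned SUV analysis.** SAP section 7.2 states: "Tumor uptake will be evaluated by the Standard Uptake Value (SUV) at each lesion by PET Imaging". It then plans summaries by location and time point, 80% and 95% confidence intervals for the SUV difference between GRPR-positive and GRPR-negative patients, and a listing of SUV ratios to reference regions.

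**How positivity is called.** SAP section 7.4 cross-tabulates lesions "where positivity will be assessed visually". Sections 7.5.1 and 7.5.2 tabulate positive and negative PET findings against histology, with no SUV cut-off.

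**What a lesion is.** The protocol synopsis refers to "tumour lesions, defined as focal areas of abnormal uptake featuring greater" SUVmax than the surrounding tissue.

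**What is logged as changed.** SAP section 11 records the added SUV ratio and one dropped comparison of lesion counts. It does not mention the threshold.

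**The concern.** A threshold needs a reference standard, an SUV metric, an imaging time point, a rule for choosing the cut-off, and SUVs from sites on both sides of it. The SAP supplies none of the first four for this purpose and leaves the last open. The study report would then either be silent on a stated objective or carry a cut-off whose ingredients were chosen after the data were seen. Such a cut-off could be carried into later studies of the tracer with overstated accuracy.

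**Working it through.** **1. Text check.** Each ingredient of a threshold analysis, set against the documents:

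| Ingredient | Protocol | SAP |
|---|---|---|
| Objective | 3.2.2 | 2.1 |
| Endpoint | SUV of each lesion (3.3.2); no cut-off | None in 3.2; the protocol's SUV-per-lesion item is also absent from that list |
| Reference standard for the cut-off | Not stated | Not stated |
| SUVmax or SUVmean | Both | Both |
| Time point | Per time point (4.1.6) | Not stated for a cut-off |
| Cut-off criterion, ROC curve, validation | None | None |
| Recorded as dropped | n/a | Not in section 11 |

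The nearest planned analysis is the SUV difference by GRPR status in SAP 7.2. A difference in location does not give a cut-off.

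**2. The plan's only precision figure.** SAP section 10 gives 66.4% to 92.7% for 25/30. The Wilson interval is (p + z²/2n ± z√[p(1−p)/n + z²/4n²]) / (1 + z²/n), with p = 0.8333, n = 30, z = 1.96.
- Centre: (0.8333 + 0.0640)/1.1281 = 0.7955.
- Half-width: 1.96 × √(0.00463 + 0.00107)/1.1281 = 0.1311.
- Result: 66.4% to 92.7%, as stated.

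This figure concerns the sensitivity of the PET call. It says nothing about an SUV cut-off.

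**3. Optimism of an uncorrected cut-off.** The assumptions here are not in the documents: one biopsied lesion per patient, SUV known at every site, normal SUV with equal SD, and the cut-off that maximises J = sensitivity + specificity − 1. An AUC of 0.80 means a separation of √2 × Φ⁻¹(0.80) = 1.19 SD, so the best attainable J is 2Φ(0.595) − 1 = 0.45. Means over 1,500 simulated data sets per setting:

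| GRPR+ / GRPR− | AUC | Apparent J | J in new patients |
|---|---|---|---|
| 40 / 10 | 0.80 | 0.565 | 0.413 |
| 30 / 20 | 0.80 | 0.539 | 0.420 |
| 40 / 10 | 0.50 | 0.198 | 0.000 |
| 8 / 2 (one tumour type) | 0.80 | 0.715 | 0.382 |

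Independent reruns of 4,000 data sets per setting agree to within about 0.01.

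**4. Effect of having SUVs at PET-visible sites only.** Further assumptions: normal log-SUV, 30 GRPR-positive and 20 GRPR-negative sites, and a site is visible when its log-SUV exceeds the true optimum (3,000 runs).
- Separation 1.0 SD: the median cut-off moves from 0.50 to 1.24 SD. The expected number of GRPR-negative sites with an SUV is 20 × (1 − Φ(0.5)) = 6.2 (simulated 6.1).
- Separation 1.5 SD: the median cut-off moves from 0.75 to 1.48 SD. The expected number is 20 × (1 − Φ(0.75)) = 4.5.

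The upward shift is about 0.7 SD in both cases. With 45 positive and 5 negative sites, the chance that no GRPR-negative site has an SUV is Φ(0.5)⁵ = 16% or Φ(0.75)⁵ = 28%.

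**The case against.** The strongest reply is that the objective is attainable. Protocol 4.1.6 states the intention and refers to a central reading manual that is not among these documents. The SAP already sends dosimetry detail to a separate report, and its section 1 allows revision before database lock. This stands against any claim that the objective cannot be met. The documents show only that the SAP does not deliver it as written. A separate manual would not replace a statistical method that protocol 7.2 assigns to the SAP.

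A reader might also infer that PET-negative lesions have no SUV. The documents do not go that far. The SAP phrase about each lesion can mean measured by PET, SAP 7.4 and 7.5.1 speak of negative as well as positive lesions, and the synopsis says all lesions are measured. SUV at visually negative sites is unspecified, not excluded.

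Nor would a cut-off necessarily be fitted on positives only. A GRPR-negative lesion that is visible on PET has an SUV on any reading, so the restriction is to PET-visible sites.

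Visual reading is not a fault in itself. It matters only because fitting an SUV cut-off to the visual call would be circular.

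The optimism simulation measures the bias of an uncorrected cut-off, not the effect of the missing analysis, and its GRPR splits and AUCs are assumed. The plan's own example has 30 GRPR-positive patients, and SAP section 7 allows for no GRPR-negative patient at all, in which case no ROC curve exists.

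Finally, all testing is exploratory and no decision rule uses the threshold, so the consequence is moderate. Even so, an exploratory threshold needs a stated method.

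**Conclusion.** The point holds in a limited form: the SAP as written has no analysis for the SUV threshold objective and does not declare it dropped. That conclusion rests on the text alone. It affects a secondary objective, not the primary one, and can be repaired before database lock.

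The likely size of the harm from a later ad hoc cut-off is illustrative. At 40/10 and AUC 0.80, J is overstated by 0.57 − 0.41 = 0.16. With no true discrimination, an apparent J of about 0.20 would still appear. If only PET-visible sites have SUVs, the cut-off moves up by about 0.7 SD under the assumptions in step 4. The documents do not support the stronger readings that the objective is unattainable or that SUV at PET-negative sites is ruled out.

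**What to change.** Before database lock, add a threshold analysis to SAP 7.2 and 7.5, with an endpoint in 3.2:

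- **Measurement.** Take SUVmax and SUVmean at the matched site of each patient's biopsied lesion, including sites that are visually negative on PET. Where linkage fails, work at organ level as SAP 7.5 already does, and state the organ-level SUV rule. Exclude sites removed by surgery before the scan.
- **Time point.** Name one imaging time point usable in both groups. No nominal time is shared: the dosimetry scan at 2 h ± 15 min spans 105–135 min, and the non-dosimetry scans span 60–120 and 120–180 min. The pairing therefore has to be written down, with a rule in case the non-dosimetry times are adjusted as SAP 2.2 allows.
- **Analysis.** With biopsy GRPR status as reference, report the ROC curve, AUC and Youden cut-off pooled over tumour types and labelled exploratory. Add patient-level bootstrap intervals and leave-one-patient-out sensitivity and specificity. Conventional-imaging lesions without a biopsy have no GRPR label and cannot enter this ROC.
- **Tumour types.** Give per-type results descriptively only, and log in section 11 that this departs from protocol 4.1.6.
- **Minimum.** State the number of GRPR-negative lesions below which no threshold is reported. As a guide, the Wilson 95% interval for an 80% specificity is 58.4–91.9% with 16/20, 49.0–94.3% with 8/10 and 37.6–96.4% with 4/5.

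If this is not wanted, record in section 11 that the objective is dropped.

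The cost is SAP wording, some extra SUV measurement by readers on existing images, and one extra analysis. No new patients or scans are needed. With few GRPR-negative lesions the result may be that no threshold is reported.
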